4.13. Protocol Deviations

A deviation is any noncompliance with the clinical trial protocol, GCP, or manual of procedures requirements. The noncompliance may be either on the part of the participant, the investigator, or the study site staff. Deviations from the protocol should be avoided. If deviations occur, The implications of the deviation must be reviewed and discussed. Investigator must document and explain protocol deviations by stating the reason, date, and the corrective action(s) taken. Deviations, for which no corrections are relevant, can be acknowledged and confirmed via edit checks in the CRF. The documentation for the protocol deviations must be kept in the Investigator's trial file and Hunazine Biotech trial master file. Major deviations from the protocol, as defined as deviations that impact participant safety or endpoints, will be promptly reported to the DSMB and Sponsor. Minor deviations from the protocol will be recorded on a source document and corresponding eCRF, and included in the annual report. Examples of minor deviations are events outside the control of the investigators (e.g., participant missed visit window or study parameters that are not part of the primary endpoint was not performed at a visit).

4.14. Study monitoring plan (monitoring visits, level of source data verification, etc.)

Trial monitoring activities will be provided by the CRO monitor(s), which will be conducted prior to beginning, at initiation, during, and at closeout of the trial by the monitor(s). At the beginning of the study, the monitor(s) will (1) verify the physical facilities of the study site. (2) ensure that the study team including the investigators and study staff are qualified and experienced. (3) provide training to study staff. During the course of the study, the monitor will visit the clinical site at regular intervals to verify compliance to the protocol; completeness, accuracy, and consistency of the data; and adherence to local regulations and requirements, including GCP on the conduct of clinical research. At a minimum the monitor(s) will do the following: (1) ensure that study staffs are performing their duties as per the delegation of authority log. (2) ensure that the study is being performed according to the protocol and applicable regulatory requirements. (3) review adherence to the protocol-specific SOPs. (4) verify source documents and eCRF are completed accurately and perform verification of eCRF against the available source documents. The monitor should have access to participant medical records and other study-related records needed to verify the entries on the eCRFs. (5) check that all AEs / SAEs and deviations have been appropriately reported. (6) ensure that each participant or parents/guardians have signed the approved ICF. (7) Ensure adequacy of study drugs and clinical trial supplies at the site. (8) review different study logs, e.g. 'delegation of authority', 'IP accountability log', 'temperature log' etc. (9) review visit findings with PI / investigator(s) and provide action items for the site personnel. (10) provide refresher training if necessary. The PI and the monitor must agree to cooperate to ensure that any problems detected in the course of these monitoring visits, including eCRF completion and query resolution, are resolved. Close-out monitoring visit includes (1) Final review of the source documents and eCRF, and resolution of missing and questionable data (2) Final 'IP accountability'; returning remaining IPss to the sponsor or destruction of remaining IPs at study site. (3) Final 'specimen accountability'. (5) Review and record site close-out report submitted to sponsor, IRB and regulatory authorities.

4.15. Regulatory Agency inspection

The PI must be aware that representatives from regulatory authorities (e.g. DGDA) or the IRB may wish to inspect the eCRFs and associated study records. The PI and study coordinator must make the relevant records available for inspection and will be available to respond to reasonable requests and audit queries made by authorized representatives of regulatory agencies.

4.16. General Considerations: Risk Management and Quality Assurance

4.16.1. Quality Tolerance Limits

A QTL is a trial-level parameter, not a patient-level parameter. Examples include inclusion/exclusion protocol violations, incomplete/missing endpoint data, and AEs/SAEs of special interest.

4.16.2. Data Quality Assurance

QA is a systematic and independent assessment of all the clinical trial activities and records. It checks for following aspects: Generation, recording, analysis, and reporting of the clinical data are in accordance with the protocol, Standard Operating Procedures (SOPs) and Good Clinical Practices (GCPs).

4.16.3. Source Data

The executive order on GCP defines source data as any information in original records and certified copies of original records of clinical findings, observations or other activities in a clinical trial necessary for the reconstruction and evaluation of the trial.

Source data may be both electronic and on paper. The following list includes examples of where source data may be stored:

- medical records
- laboratory reports
- diaries
- dispensing logs
- Any research records
- Case Report Forms (CRF)
- ECG printouts
- X-ray images
- radiological reports, etc.
- communication: verbal

5.0 Sample Size Calculation and Outcome (Primary and Secondary) Variable(s)

Clearly mention your assumptions. List the power and precision desired. Describe the optimal conditions to attain the sample size. Justify the sample size that is deemed sufficient to achieve the specific aims.

Planned screening is 500 participants. ITT (intention to treat) group is 150 patients. Enrollment will stop once 150 participants are recruited, or once 100% of per-protocol dataset (PP) is achieved. Sample size was calculated based on the mean volume of stool output in cholera patients. Mean stool output was assumed at 280 ± 156 g/kg²²⁻²⁴. Assuming 33% reduction (alternative hypothesis) vs no reduction (null hypothesis), sample size was calculated using GraphPad Prism software for two-tailed t-test with alpha 5% and power 0.8. Using recruitment of 50 participants per arm (100 total), power level of 0.82 can be achieved. Although, this is a sufficient level of power for the projected study, data points lost due to participant drop-out, cross-over to other study arms, withdrawal and missing data will affect the power of the study. We calculated that recruitment of up to 75 patients per study arm would allow power of 0.94.

Endpoints associated with primary and secondary objectives, and justification for endpoints are given below (Table 1).

Table 1-Primary and Secondary Objectives and Endpoints

OBJECTIVES	ENDPOINTS	JUSTIFICATION FOR ENDPOINTS
Primary		

 To assess the efficacy of VR-AD-1005 for the treatment of acute diarrhea in cholera patients in combination with standard treatment (rehydration and antibiotics, please see attached SoP for more details) versus standard treatment with placebo. Efficacy is measured as reduction in stool output between the start of treatment until final diarrheal stool before clinical recovery (defined as disappearance of watery stool and two consecutive passages of soft stool) or end of study treatment (treatment duration 72 hours), which is earlier. 	
 Reduction in stool output volume (ml/hour/kg) over a treatment period measured as stool weight and recalculated to stool volume using 1:1 w/v ratio, and plotted as stool output quantity per each 12-hour period for the duration stool collection. 6 points are expected for a 72-hour stool collection. Measurement of stool output will be performed by collecting the stool from a participant into the pre-weighed vessel. The vessel with stool will be weighed on the calibrated scale, the weight of the vessel would be subtracted, and the resulting stool weight recorded into the stool diary form. During weighing of stool, Infection Prevention and control (IPC) standards will be upheld by implementing protection of personnel via using appropriate personal protective equipment. Hand washing before and after stool weighing will be strictly adhered to thereby preventing infection of study personnel. After weighing, stool will be disposed of as biohazardous waste at study sites and the weighing vessel appropriately disinfected before next measurement or discarded, if disposable. 	
 Primary endpoint allows to monitor and characterize the efficacy of VR-AD-1005 for reduction of stool output. Over-secretion of hypotonic fluid occurs predominantly in the small intestine, and fluid is lost with stool. The volume of fluid loss in cholera patients can be life-threatening due to rapid dehydration. Thus, the primary efficacy endpoint is designed to demonstrate potential of VR-AD-1005 treatment to reduce fluid loss with stool.
Secondary		

 Assessments of improvement of hydration status, fluid input and duration of 	
 Time until the stool volume output reduction to 200 ml/hour or less. Duration of stool output in excess of 200 ml/hour per patient will be recorded between the start and end of 	
 Secondary end-points are designed to supplement the primary end-point by providing a


diarrhea following VR-AD-1005 administration.
 
 • Evaluation of safety and tolerability of VR-AD-1005 in addition to standard of care (SoC) versus SoC with placebo in adults with symptomatic cholera via documentation of adverse events, physical examination, and vital signs. 	
the treatment for both treatment groups.
 
 • Time until clinical recovery (defined as disappearance of watery stool and two consecutive passages of soft stool). Duration of diarrhea until the passage of first non-watery stool (soft/loose) or no stool for 12 hours or the end of treatment (72 hours) will be derived from date and time records in daily stool charts. • Number of subjects with clinical recovery as above within treatment group. The number of subjects with clinical recovery will be recorded as total for the entire treatment duration, and as number of recoveries per each 24-hour period of treatment. • Number of unscheduled IV rehydration episodes per treatment. The number of unscheduled IV rehydration episodes per treatment will be recorded for the entire duration of the treatment. Unscheduled IV rehydration is defined as "receipt of IV fluid during the maintenance phase of hydration due to development of severe dehydration or some dehydration with high purging (>15 ml/kg/hour) or persistent vomiting (>3 episodes/hour), or failure to take ORS for any reason" • Duration of IV rehydration for the entire treatment period per treatment group and per each 24- hour period of treatment. • Safety will be measured by the proportion of patients that will present with AE/SAE as defined in Appendix II following administration of VR-AD- 1005. 	
measure of hydration status of the participants, as well as providing a measure of the duration of the illness. Dehydration is the primary cause of death in cholera; duration of illness is the primary measure of the burden on the healthcare system and quality of life/productivity loss for cholera patients. Assessment of reduction in the need for unscheduled intravenous rehydration and time until switch to oral rehydration therapy will allow to assess the benefit of VR-AD-1005 for in-patient management of cholera cases. Thus, secondary end-points allow to characterize the benefits related to potential improvements in the clinical course of the disease, case management and quality of life for cholera patients.

---	--	--

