6.0 Data Analysis

Describe plans for data analysis, including stratification by sex, gender and diversity. Indicate whether data will be analysed by the investigators themselves or by other professionals. Specify what statistical software packages will be used and if the study is blinded, when the code will be opened. For clinical trials, indicate if interim data analysis will be required to determine further course of the study.

Data analysis must comply with ICH E9 Guideline and ICH E9(R1) Guideline. All relevant data collected in the trial should be considered in the statistical considerations section.

The analysis will be conducted on all participant data at the time the trial ends.

Statistics for primary end-point data and parametric secondary end-point data will be presented via means (alternatively, LSMEANS) with standard deviations; primarily two-tailed Student's t-test will be used for analysis with significance level of $p \leq 0.05$. For non-parametric analysis, such as lifetime data, Kaplan-Meier analysis will be used with significance level of $p \leq 0.05$. Some data might be expressed and analyzed as % values, such as the occurrence of unscheduled IV rehydration.

Analysis of secondary endpoints will be performed through the same method of the primary endpoint, which is found via a one- sided two sample unequal variance Student's t-test. The scale for each secondary endpoint will be nominal and will be determined at a single endpoint, which is at the end of intervention. The results will be presented by LSMEANS (Least-squares Means) with standard errors.

Primary Endpoint:

Reduction in stool output volume (ml/hour) over a treatment period measured and plotted as total stool output during 12-hour stool collection at every 12 hours for 72 hours.

Secondary Endpoints:

- Time until the stool volume output of 200mL/hour or less. Duration of stool output in excess of 200mL/hour per patient will be recorded between the start and end of the treatment for both treatment groups.
- Time until recovery. Duration of diarrhea until the passage of first non-watery stool or no stool for 12 hours or the end of treatment (72 hours) will be derived from date and time records in daily stool charts.

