6.2. Analysis Supporting Primary Objectives

6.2.1. Statistical Model, Hypothesis, and Method of Analysis

Primary Endpoint:

Reduction in stool output volume over a treatment period.

Primary Endpoint 1., Hypothesis 1. Treatment with VR-AD-1005 reduces stool output in patients with diarrhea due to *V. cholerae* infection. Null hypothesis is stated as no statistically significant difference in stool output volume as compared to placebo; alternative Hypothesis 1 is stated as statistically significant reduction in stool output volume in patients treated with VR-AD- 1005.

Two analytical approaches are proposed. Approach 1 will be based on the total quantity of stool purged by participant during the intervention administration period. Stool output will be expressed as g/kg body weight based on the stool charts, and the means will be compared between intervention and placebo groups using Student's unpaired t-test. In approach 2, stool purging is measured and plotted as total stool output in ml/kg/12 hours based on the individual stool collection charts. Weight of stool will be converted to volume using 1:1 weight/volume ratio. Diarrhea of cholera resolves rapidly, and majority of patients are expected to recover within 30-50 hours after randomization. 12-hour analysis increments allow a better insight into the onset and timing of the effect of study intervention as compared to cumulative data over the duration of the treatment. Means will be compared for each 12-hour period after first intervention administration using unpaired Student's t-test. Normal distribution is assumed for both cases. Analysis will be conducted in the ITT, MITT and PP groups. Missing data and outliers will be handled using imputation technique. Non-adherence and lost to follow-up patients will be categorized into the appropriate group and handled accordingly. No subtractions will be made from the ITT group after randomization assignment.

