6.3. Analysis Supporting Secondary Objectives

Analysis of secondary end-points is not dependent on the analysis of the primary end-point.

Secondary Endpoint 1, Hypothesis 2. Treatment with VR-AD-1005 improves hydration control in patients with diarrhea due to *V. cholerae* infection. Null hypothesis is stated as no statistically

significant difference in the number of unscheduled hydration episodes as compared to placebo; alternative hypothesis 2 is stated as statistically significant improvement in hydration control, expressed as number of unscheduled rehydration episodes over the treatment period; in patients treated with VR-AD-1005. Unscheduled IV rehydration is defined as “receipt of IV fluid during the maintenance phase of hydration due to development of severe dehydration or some dehydration with high purging (>15 ml/kg/hour) or persistent vomiting (>3 episodes/hour), or failure to take ORS for any reason”

Secondary Endpoint 2, Hypothesis 3. Treatment with VR-AD-1005 shortens duration of diarrhea in patients with diarrhea due to *V. cholerae* infection. Null hypothesis is stated as no statistically significant difference in the duration of diarrhea as compared to placebo; alternative hypothesis 2 is stated as statistically significant reduction in the duration of diarrhea, expressed as number of days till normalization of stool, in patients treated with VR-AD-1005.

Secondary Endpoint 3, Hypothesis 4. Treatment with VR-AD-1005 shortens duration of stool output in excess of 200ml/hour in patients with diarrhea due to *V. cholerae* infection. Null hypothesis is stated as no statistically significant difference in the duration of stool output >200 ml/hour as compared to placebo; alternative hypothesis 2 is stated as statistically significant reduction in the duration of diarrheal output >200 ml/hour, expressed in hours, in patients treated with VR-AD-1005.

Analysis:

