Secondary Endpoint 1, assessment of hydration control. There are two measurable parameters to be assessed in the patient hydration. Parameter 1 is the number of unscheduled hydration episodes. The numbers will be derived from the individual rehydration records, and the number of patients receiving IV rehydration will be expressed in % and compared for control and study intervention group. Alternatively, total number of IV rehydration episodes can be expressed as means for control and study intervention group and analyzed using Student's t-test. Parameter 2 is the volume of the oral rehydration solution received during the course of interventional treatment. Total volume of rehydration solution (oral and IV where applicable) will be derived from the individual rehydration records, expressed in ml/kg of patient weight, and analyzed as means using unpaired Student's t-test. Analysis subgroups will include 1) total hydration received over the course of study after first administration of interventional medication, and 2) hydration received during first 12 hours and 3) hydration received during first 24 hours.

Secondary Endpoint 2. Assessment of duration of diarrhea. Total duration of diarrheal illness is an important parameter in the assessment of antidiarrheal treatment efficacy. Study intervention is expected to reduce the overall duration of the diarrhea. Duration of diarrhea is assessed from first administration of study intervention until the termination of diarrhea, which is defined as first formed stool, or no stool for 12 consecutive hours. Duration of diarrhea will be derived from individual stool charts. Kaplan-Meier survival curves will be built to compare duration of diarrhea between control and intervention groups.

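### The primary stool count ends at recovery in one section and at 72 hours in another, post-recovery windows and the rate denominator are undefined, and the definitions of recovery conflict

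*Combined protocol and SAP*

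**What the plan says.** **Where counting stops.** The primary objective in Table 1 (section 5.0) begins the count when treatment starts and runs it "until final diarrheal stool before clinical recovery (defined as disappearance of watery stool and two consecutive passages of soft stool) or end of study treatment" at 72 hours, whichever is earlier. The endpoint beside it adds that "6 points are expected for a 72-hour stool collection". Section 6.0 gives the primary endpoint with no recovery cut-off: "plotted as total stool output during 12-hour stool collection at every 12 hours for 72 hours". Section 4.5.2 collects stool throughout treatment, but section 4.0 lets treatment finish early on recovery. Section 4.3 keeps everyone on the ward for three days and rules out early discharge, and Appendix I assesses stool output at every time point through Day 3.

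**What is analysed.** Table 1 names a rate: "Reduction in stool output volume (ml/hour/kg) over a treatment period measured as stool weight". Section 6.0 uses ml/hour. Section 6.2.1 gives two approaches: total g/kg over the administration period, and ml/kg per 12 hours with a t-test in each window. The sample size uses a total, 280 (SD 156) g/kg. Section 6.2.2 lets missing values be dropped below 5% and otherwise calls for multiple imputation in the ITT population.

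**When recovery is expected.** Section 6.2.1: "majority of patients are expected to recover within 30-50 hours after randomization". Section 6.3 puts the average duration at 30-35 hours.

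**How the end of diarrhoea is defined.**
- Table 1, primary objective and time to recovery: two soft stools in a row.
- Table 1, same time-to-recovery bullet: "Duration of diarrhea until the passage of first non-watery stool (soft/loose) or no stool for 12 hours or the end of treatment (72 hours"). Section 6.0 is similar.
- Section 6.3, analysis of Secondary Endpoint 2: "which is defined as first formed stool, or no stool for 12 consecutive hours".
- Section 6.3, Hypothesis 3: "expressed as number of days till normalization of stool".

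**The concern.** A 12-hour window that falls after recovery can be handled in three ways, and the plan chooses none of them.

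- **Zero or measured weight:** every randomised patient stays in the comparison.
- **Left out:** later windows compare only patients still purging. If the drug shortens diarrhoea, that group is selected after randomisation, and differently in each arm.
- **Missing:** the 5% rule would trigger imputation, and recovered patients would be given modelled stool they never passed.

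The rate has the same gap. If it is divided by the patient's own diarrhoeal hours, the denominator is something the drug is meant to shorten. Divided by a fixed 72 hours, it is the total rescaled.

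Separately, the definitions of recovery give different times from one stool chart, so time to recovery and the number recovered depend on which section the analyst follows. If these choices stay open until the data are unblinded, they can be made with the results in view.

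**Working it through.** **1. The plan's own figure.** Inputs from section 5.0: mean 280, SD 156, 33% reduction, two-sided alpha 5%. Difference = 0.33 × 280 = 92.4 g/kg. Noncentrality = (92.4/156) × √(n/2), which is 2.96 at 50 per arm and 3.63 at 75. Noncentral-t power is 0.835 and 0.950, against the stated 0.82 and 0.94. With the difference rounded to 90 g/kg it is 0.815 and 0.939. The stated power is therefore reproduced, for total g/kg; none is given for a rate in ml/hour/kg.

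**2. Who is still purging in the late windows.** The documents give no SD for duration, so I assume lognormal durations with coefficient of variation (CV) 0.3, 0.5 or 0.7. Share still purging at time t = 1 − Φ((ln t − μ)/σ), with σ² = ln(1 + CV²) and μ = ln(mean) − σ²/2. Example with mean 35 h, CV 0.5, t = 48: σ = 0.472, μ = 3.444, z = (3.871 − 3.444)/0.472 = 0.90, share 18%.

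| Mean duration | 36 h | 48 h | 60 h |
|---|---|---|---|
| 30-35 h (section 6.3) | 22-40% | 4-21% | 1-12% |
| 50 h (top of the range in 6.2.1) | 58-83% | 40-50% | 22-27% |

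At the plan's average, 48 hours leaves about 3 to 16 of 75 patients per arm under the Table 1 cut-off. The 36-48 h window depends on the assumed mean. At 30-35 h, 79-96% have recovered by 48 hours, so if those windows were coded missing, the 5% limit would be far exceeded.

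**3. What the choice does to power.** Simulation of 1,500 trials per scenario, 75 per arm. Control duration is lognormal, mean 35 h, CV 0.4, capped at 72 h. Each patient purges at a constant rate, mean 280/35 = 8 g/kg/h. The CV of the rate is set so that the total has CV about 156/280 = 0.557: √((1 + 0.557²)/(1 + 0.4²) − 1) = 0.36. If two or fewer patients contribute in an arm, the window counts as no rejection. Window cells show recovered patients at zero / dropped.

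| Measure | Duration −33% only | Rate −33% only | Both −18% |
|---|---|---|---|
| Total g/kg, or total ÷ 72 h | 0.99 | 0.99 | 0.99 |
| Rate over own diarrhoeal hours | 0.05 | 1.00 | 0.92 |
| 24-36 h | 1.00 / 0.54 | 0.80 / 0.95 | 0.96 / 0.80 |
| 36-48 h | 0.99 / 0.11 | 0.30 / 0.58 | 0.81 / 0.28 |
| 48-60 h | 0.81 / 0.01 | 0.10 / 0.22 | 0.48 / 0.08 |
| 60-72 h | 0.25 / 0.00 | 0.04 / 0.06 | 0.14 / 0.01 |

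The third scenario gives 1 − 0.82² = 33% overall. The 0.05 is the test's type I error, because that scenario leaves the hourly rate unchanged. Power for the total exceeds the stated 0.94 because a proportional effect also shrinks the SD in the active arm and because stool is capped at 72 h; read only the contrasts.

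**4. One chart, several recovery times.** Take an invented patient with the last watery stool at hour 30, soft stools at 34 and 40, and a formed stool at 50. The first soft or loose stool gives 34 h, two soft stools in a row give 40 h, and the first formed stool gives 50 h. Normalization is undefined. A second invented patient passes nothing after hour 30. That patient meets the 12-hour rule by hour 42 but never meets the two-soft-stools rule.

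**5. Reaching 72 hours.** If everyone still ill at 72 h is counted as an event there, all at risk have the event together, so that time adds nothing to a log-rank statistic. The damage is to the curve and to the number recovered, which would read 100%.

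**The case against.** The strongest reply is that the plan can be read as measuring everyone to 72 hours. Patients stay on the ward partly for endpoint measurement, Appendix I schedules stool assessment through Day 3, and section 6.0 has no cut-off. On that reading a recovered patient has a measured weight, often zero, and nothing is missing. In addition, neither approach in section 6.2.1 divides by the patient's own diarrhoeal time, and both Approach 1 and the Kaplan-Meier analysis would show shorter diarrhoea.

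Much of this stands, and it rules out several stronger conclusions that a reader might draw:

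- **That most patients have no data after recovery.** This holds only under the Table 1 cut-off, or if collection ends with treatment on recovery.
- **That imputation will invent stool.** No section classes a post-recovery window as missing.
- **That the hourly rate hides any benefit.** The denominator is unstated, and the loss is complete only if it is the patient's own diarrhoeal time and the drug affects duration alone. With the effect split, power is 0.92 against 0.99.
- **That the conflicting recovery rules empty the windows.** The cut-off does that. The primary objective carries a single recovery rule; the others belong to the duration endpoint.
- **That expressing duration in days loses precision.** Times come from dated and timed charts, and no rounding is stated.

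Zero-filling is not always the more powerful choice either: if only the rate falls, dropping recovered patients does better at 36-48 h (0.58 against 0.30). The reason to count zeros is that they are what was observed and they keep the randomised groups intact.

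What the reply does not remove is the contradiction between Table 1 and section 6.0. Approach 1 does not settle it, because it covers the administration period, which section 4.0 allows to end at recovery.

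**Conclusion.** The point holds as a contradiction in the primary endpoint together with two missing rules, and it should be settled before unblinding. Table 1 and section 6.0 end the count at different times; post-recovery windows have no coding rule; the rate has no denominator. At the stated 30-35 h average, the Table 1 cut-off would leave 4-21% of patients contributing at 48 h and 1-12% at 60 h. The 36-48 h window may also be thin, but that rests on the assumed distribution. If the drug mainly shortens diarrhoea, the unstated choices move power from 0.99 to 0.11 in the 36-48 h window, and from 0.99 (total) to 0.05 (own-time rate). These figures assume lognormal durations, constant individual rates and a 35 h control mean. The total keeps power 0.99 under all three mechanisms and is the quantity on which the sample size rests.

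The conflict between recovery definitions needs no assumption: the rules differ as written and give different times from the same chart.

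**What to change.** - **Primary endpoint.** In Table 1, 6.0 and 6.2.1, state one measure: total stool in g/kg from first dose to 72 hours in every participant. Weigh stool to 72 hours whenever recovery occurs. After recovery enter the measured weight, or zero if none is passed, and do not impute it. Keep section 6.2.2 for stool that was passed or may have been passed but was not weighed.
- **12-hour windows.** Apply the same rule and label these analyses supportive. If a rate is reported, state a fixed denominator.
- **Recovery.** Reconcile Table 1, 6.0 and 6.3 to one endpoint definition, chosen by the clinical team, saying how a patient who stops passing stool is classified. Analyse time to recovery in hours by Kaplan-Meier with a log-rank test, censoring patients not recovered by 72 hours and not counting them as recovered.
- **Treatment period.** Reconcile sections 4.0, 4.3 and 4.5.2 on when treatment and stool collection end. The endpoint change needs no change to treatment.

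The cost is protocol and SAP wording plus a few extra stool weighings in patients who are already inpatients. The sample size calculation is already in total g/kg and keeps that basis.
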